### 12.3.1.2. Ranked Secondary Endpoints

After the primary endpoint is successfully reached, the ranked secondary efficacy endpoints will each be tested with a 2-sided confidence interval with 0.05 Type I error in a hierarchical manner in the rank order as in [Table 8](#). The ranked secondary endpoints are:

1. Mean of averaged percent area of StrataGraft treatment site closed per subject at Week 12 without autograft placement
2. Number (%) of confirmed complete wound closures of the StrataGraft treatment sites on or before Week 12 without autograft placement
3. Mean of averaged percent area of StrataGraft treatment site autografted by Week 12

For continuous efficacy endpoints, missing data will not be imputed. Missing or incomplete binary variables will be imputed as failures. Missing data are anticipated to occur only if the subject is lost to follow-up because information can be obtained for a missing visit when the subject returns for a subsequent visit. If a subject has autograft placement, the data collected after the autograft placement will be censored.

The averaged percent area closed per subject at Week 12 will be calculated as (Sum of percent area closed across treatment sites for a subject at Week 12/the total number of treatment sites on a subject).

The percentage of StrataGraft treatment sites with confirmed complete wound closure on or before Week 12 will be calculated as [(Total number of StrataGraft treatment sites with confirmed complete wound closure without autografting on or before Week 12/Total number of treatment sites) x 100].

The averaged percent area of StrataGraft treatment sites per subject autografted by Week 12 will be calculated as (Sum of percent area of StrataGraft treatment sites per subject autografted by Week 12/the number of treatment sites on that subject). It is a cumulative sum of percent area autografted for all nonmissing visits on or before Week 12.

The summary statistics with 95% confidence interval (CI) and p-value based on null hypothesis specified in [Table 8](#) for each endpoint from t-distribution will be presented based on the ITT population by designated treatment site and pooled designated treatment site. The analyses by age cohort will be presented.

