### 12.3. Statistical Analyses

This section provides a general summary of the statistical methods to be used in analyzing study data. A more detailed statistical analysis plan (SAP) will be provided in a separate document that will be finalized prior to database lock. SAS version 9.4 or newer will be used.

Descriptive statistics for continuous variables will include the mean, median, standard deviation, minimum value, and maximum value. Categorical data will be summarized by counts and percentages.

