To evaluate whether StrataGraft treatment eliminates or reduces the need for autografting and promotes wound closure in a pediatric population with thermal burns that contain intact dermal elements and for which autografting is clinically indicated.	All enrolled subjects who received StrataGraft	$H_0$ : The response rate of primary endpoint is less than or equal to the 50% $H_1$ : The response rate of the primary endpoint is greater than the 50%  Positive study criteria: The lower bound of primary endpoint 95% CI derived from the normal approximation to the binomial $> 50\%$ .	Percentage of subjects achieving confirmed complete closure of all StrataGraft treatment sites on or before Week 12 without autograft placement. Confirmed complete wound closure is defined as 100% re-epithelialization confirmed at 2 visits at least 2 weeks apart but before Week 20.	Early discontinuation due to: 
 
• Withdrawal of informed consent
 
• Lost to follow-up
 
• Adverse event
 
• Investigator decision
 
• Death
 
• Other
 
 Missing/incomplete data will be imputed as failure (ie, no confirmed complete wound closure).

CI = Confidence Interval; LB = Lower Bound

**Table 8: The Objective, Population, Hypotheses, Endpoints and Intercurrent Events and Data Handling for Ranked Secondary Efficacy Endpoints**

Objectives	Population	Hypotheses	Endpoints	Intercurrent events and data handling
To evaluate the mean averaged percent of wound area closure of StrataGraft treatment site without autograft placement at Week 12	All enrolled subjects who received StrataGraft	$H_{01}$ : Mean of averaged percent wound area closure of StrataGraft treatment site without autograft placement at Week 12 $\leq 50\%$ $H_{11}$ : Mean percent of wound area closure of StrataGraft treatment site without autograft placement at Week 12 $> 50\%$	Mean of averaged percent area of StrataGraft treatment site closed without autograft placement at Week 12	
Early discontinuation due to:
 
 
• Withdrawal of informed consent
 
• Lost to follow-up
 
• Adverse event
 
• Investigator decision
 
• Death
 
• Other
 
 
Missing/incomplete continuous variables will not be imputed.

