### **12.3.3. Handling of Missing Data**

Subjects will be encouraged to return to clinic for each scheduled visit. Direct observation of the wound and collection of data at scheduled times is essential to ensure the quality of the data. However, should a visit be missed, thereby resulting in missing data for that visit, the following approaches will be employed to manage the missing data.

For the primary efficacy endpoint, missing/incomplete data will be imputed as failure (ie, no confirmed complete wound closure).

For the ranked secondary endpoints, missing/incomplete data will not be imputed.

A full description of missing data imputation methods for all endpoints will be described in detail in the SAP.

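### Applied literally, the censoring rule drops a single-site subject autografted before Week 12 from secondary endpoint 1 instead of counting the graft against it

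*Combined protocol and SAP*

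**What the plan says.** All references are to the protocol unless the SAP memo is named.

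- **Endpoint and population.** Section 12.3.1.2 and Table 8 define secondary endpoint 1 as the mean, over subjects, of averaged percent area closed at Week 12 without autograft. The population is all enrolled subjects who received StrataGraft.
- **Per-subject value.** It is calculated as "Sum of percent area closed across treatment sites for a subject at Week 12/the total number of treatment sites on a subject". For a subject with one site, this is that site's Week 12 value.
- **After an autograft.** "If a subject has autograft placement, the data collected after the autograft placement will be censored".
- **Missing continuous data.** Section 12.3.1.2: "For continuous efficacy endpoints, missing data will not be imputed". Table 8: "Missing/incomplete continuous variables will not be imputed". Section 12.3.3: "For the ranked secondary endpoints, missing/incomplete data will not be imputed".
- **Missing binary data.** By contrast, Section 12.3.1.2 says "Missing or incomplete binary variables will be imputed as failures".
- **Intercurrent events.** Table 8 lists reasons for early discontinuation. Autograft is not among them.
- **Deferred detail.** Section 12.3 opens with "This section provides a general summary of the statistical methods to be used in analyzing study data", and Section 12.3.3 promises that "A full description of missing data imputation methods for all endpoints will be described in detail in the SAP". The SAP memo plans listings for one subject and contains no such description.

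**The concern.** On this endpoint, needing an autograft is an unfavourable treatment outcome: grafted area has not closed without a graft. It is not a gap in the data. The censoring sentence together with the no-imputation rule treats it as a gap. For a single-site subject grafted before Week 12, the only value that enters the formula is removed and nothing replaces it. Binary endpoints have a failure rule for this situation; continuous ones do not.

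The estimate is what is at stake. If grafted subjects leave, the mean and its confidence interval describe children who did not need a graft, while the table says they describe all treated children. The bias is upward whenever grafted subjects would have scored below the rest.

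Subjects with several sites are also unsettled. Take three sites, one grafted and two fully closed. If censoring is per subject, the subject has no value. If only the grafted site is censored and the divisor stays at three, the subject scores (0 + 100 + 100)/3 = 66.7%.

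**Working it through.** **1. The plan's own figure.** Section 12.1 claims more than 90% power for the primary endpoint with 50 subjects, a null of 50% and a true rate of 83%. Under the normal-approximation rule, the lower 95% limit reaches 50% from 32 responders of 50, and exact binomial power at 83% is 0.9997. With 40 subjects the threshold is 26 and power is 0.998. Both agree with the claim. The documents give no power or expected value for secondary endpoint 1.

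**2. Size of the bias.** Let g be the proportion grafted, m the mean closure in ungrafted subjects and s the score of a grafted site, with one site per subject.

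- Drop-out mean: m
- All-subject mean: (1 − g)m + g·s
- Overstatement: g(m − s)

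The documents give no pediatric graft rate. Section 6.2 reports that more than 95% of adults closed without autografting, so g = 4% is used, with 10% as an assumed higher case. m = 95% is assumed.

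| Grafted | s = 0% | s = 50% | s = 90% |
|---|---|---|---|
| 4% | 0.04 × 95 = 3.8 | 0.04 × 45 = 1.8 | 0.04 × 5 = 0.2 |
| 10% | 0.10 × 95 = 9.5 | 0.10 × 45 = 4.5 | 0.10 × 5 = 0.5 |

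**3. Illustrative intervals (95%, t-based, 50 subjects).** Assumed data for two grafts are 38 subjects at 100%, 10 at 75% and 2 at s. For five grafts they are 36 at 100%, 9 at 75% and 5 at s. If the subjects at 100% are the primary responders, both sets pass the primary: lower limits are 64.2% for 38/50 and 59.6% for 36/50.

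| Grafted | Drop-out | Kept, s = 0% | Kept, s = 50% | Kept, s = 90% |
|---|---|---|---|---|
| 2 | 94.8 (91.8–97.8) | 91.0 (85.0–97.0) | 93.0 (89.2–96.8) | 94.6 (91.7–97.5) |
| 5 | 95.0 (92.0–98.0) | 85.5 (76.9–94.1) | 90.5 (85.8–95.2) | 94.5 (91.7–97.3) |

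With two grafts, the drop-out interval excludes the all-subject mean only at s = 0%. With five, it does so at 0% and 50%. At 90% it never does.

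**4. Effect on the test against 50%.** The secondaries are tested only after the primary succeeds. The worst case is the smallest primary success, with every non-responder grafted and scored 0% and every responder still fully closed at Week 12.

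- 32/50 (primary lower limit 50.7%): 32 at 100% and 18 at 0% give 64.0% (50.2–77.8). The test still succeeds.
- 26/40 (primary lower limit 50.2%): 26 at 100% and 14 at 0% give 65.0% (49.6–80.4). The test fails, whereas with drop-out the remaining 26 are all at 100%.
- 27/40: 67.5% (52.3–82.7). The test succeeds.

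Forty is a possible final size, because Section 12.1 lets the sponsor close the study once the younger cohort has 40 subjects.

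**5. Can the data support a better score?** Percent re-epithelialized is recorded for the whole site (Sections 10.3 and 11.3.2), and grafted area is measured at the procedure (Section 11.3.3). With p percent re-epithelialized and a percent ever grafted, the area closed without graft lies between max(0, p − a) and min(p, 100 − a). For p = 90 and a = 30 the range is 60% to 70%. At p = 100 both bounds equal 100 − a.

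**The case against.** The strongest objection is that the authors did not mean grafted subjects to be missing. Just before the censoring sentence, Section 12.3.1.2 says it expects missing data only through loss to follow-up, which would be wrong if a graft created a missing value. The same section bases the analysis on the ITT population, and Table 8 names all treated subjects. The endpoint is closure without autograft, and the divisor is all of the subject's sites, so a grafted site could be read as adding zero. All of this stands as evidence of intent. It rules out saying that the plan clearly means to exclude grafted subjects. None of it assigns a score, however, and the explicit instruction is to censor.

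A second objection is that Section 12.3 is only a summary and the detail was left to the SAP. That is fair as history: the trial stopped after one subject and the SAP became a listings memo. The gap remains in the protocol.

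A reader might also infer that the test against 50% would succeed wrongly, or that autografts disappear from the trial. The documents do not support either as a general claim. The primary gate protects the test at 50 subjects, and the exception needs exactly 26 of 40 responders with every other subject grafted and scored zero. Grafts still count against the primary and secondary endpoint 2, and secondary endpoint 3 measures grafted area.

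**Conclusion.** The point holds as a defect in the protocol's rule. Literal application removes a single-site subject grafted before Week 12 from a mean that is defined for all treated subjects, and no document supplies the score that would prevent this. Wording that favours keeping the subject makes the plan ambiguous; it does not settle the matter.

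The overstatement is 0.2 to 3.8 points at 4% grafted and 0.5 to 9.5 points at 10%. These figures rest on one site per subject, 95% closure in ungrafted subjects, and grafted sites scoring between 90% and 0%. The adult figure in Section 6.2 points to the lower graft rate. The harm is to the estimate and its interval; the test could change only in the 40-subject corner case.

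It would be wrong to infer that a published result is biased. The SAP memo states that one subject was enrolled and plans no formal analyses. The point is minor, and matters if this protocol is reused.

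**What to change.** For secondary endpoint 1 and the exploratory Week 8 endpoint, which carries the same no-autograft qualifier, replace the censoring sentence with a scoring rule:

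- Every treated subject stays in the mean.
- From autograft onward, autografted area counts as not closed without autograft. Ungrafted area and the subject's other sites keep their observed closure.
- For each site, the value is percent re-epithelialized minus percent of the site ever autografted, floored at 0. Each area counts once, so a repeat graft of the same area is not subtracted twice.
- State that this is a lower bound until the whole site is closed. Report a sensitivity analysis that scores a grafted site 0%.

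List autograft in Table 8 as an intercurrent event with this handling. State that secondary endpoint 3 counts all autografted area through Week 12.

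Do not apply the subtraction to the exploratory closure endpoint from Day 21 to Month 12. It has no such qualifier, and subtracting would redefine it.

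**Cost.** A short rule in Section 12.3.1.2 and one entry in Table 8. Percent re-epithelialized and grafted area are already collected. Removing the slack in the lower bound would need one more eCRF item, closure of the ungrafted part. The reported mean becomes slightly less favourable. No output planned in the SAP memo changes.

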### 7.1. Subject Inclusion Criteria

An included subject will be or have:

1. Aged 2 to 17 years, inclusive, as of the time of consent.
2. Written informed consent from parent(s) or legal guardian(s) and assent from the child when appropriate, as determined by the Institutional Review Board (IRB), consistent with regulatory criteria and requirements.
3. Sufficient healthy skin identified and reserved as a donor site in the event that the StrataGraft treatment site(s) requires autografting.
4. Thermal burns of no more than 30% TBSA.
5. Consenting adult(s) is/are able and willing to attend/bring child to the scheduled visits and comply with study procedures.
6. Study treatment area(s) that is/are: a) DPT in depth (ie, containing dermal elements) and for which excision and autografting are clinically indicated, as assessed by the investigator, and b) located on the torso or extremities.
7. Study treatment area of 0.5% to 10% TBSA, which may be composed of up to 3 non-contiguous areas located on the same extremity or plane of the torso.

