### **10.3. Treatment Days 7, 14, and 21 ( $\pm$ 2 days), Day 28 ( $\pm$ 3 days), and Weeks 5 - 11 ( $\pm$ 3 days)**

Subjects will be assessed weekly until complete wound closure of study treatment site(s) is/are confirmed. The following assessments or procedures will be performed at those visits:

- Obtain vital signs (Section 11.2.4).
- Remove all dressings and expose study treatment site(s). Reapply dressings, if necessary, after all wound assessments are complete.
- Photograph all study treatment site(s) (Section 11.3.4). Photographs may be taken by study site personnel, or by trained caregivers if the subject is not able to attend the study site.
- Assess each study treatment site for:
  - Signs and symptoms of infection and, if infection is suspected, assess and treat as outlined in Section 11.3.6 and Section 11.9.1.5.
  - The percent re-epithelialized of the study site until complete closure is noted (Section 11.3.2).
  - Autograft placement on study treatment site since last study visit, noting area autografted, if any; placement is assessed until complete closure is noted (Section 11.3.3).
  - Complete closure and, if closed, confirm the maintenance of closure at the next visit (Section 11.3.2). After the first observation of closure, confirmation of wound

closure will be done at a second visit at least 2 weeks after initial observation but no later than Week 20.

- Assess pain at the study treatment site(s) using the EVENDOL (observer or parent) or FPRS (subject) rating scale (Section 11.7).
- Document reason(s) for continued hospitalization if subject has not been discharged (Section 11.8).
- Update any changes to concomitant medications and/or procedures, including any readmission to hospital related to the study wound(s) or scar management measures (Section 11.4).
- Abstract from the medical record results of any safety laboratory results (ie, CBC with differential and CMP) performed since prior visit (Section 11.5). If no recorded values in medical record from Day 28 through Week 11, samples for CBC with differential and CMP may be collected during a clinically necessary venipuncture. Only 1 post-baseline sample per subject is needed.
- PRA and anti-BSA antibody samples may be collected at any visit after Week 6, but only if they may be collected during a clinically necessary venipuncture (Section 11.6). Only 1 post-baseline sample per subject is needed.

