### **11.3.3. Area of the Study Sites Autografted**

The area of each StrataGraft treatment site that is autografted will be measured during the autografting procedure. Details about obtaining wound measurements is provided in the Manual of Procedures.

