To evaluate the number (%) of StrataGraft treatment sites with confirmed complete wound closure without autograft placement on or before Week 12	All enrolled subjects who received StrataGraft	$H_{02}$ : The response rate of StrataGraft treatment sites with confirmed complete wound closure without autograft placement on or before Week 12 is less than or equal to the 50% $H_{12}$ : The response rate of StrataGraft treatment Sites with confirmed complete wound closure without autograft placement on or before Week 12 is greater than the 50%	Number (%) of StrataGraft treatment sites with confirmed complete wound closure without autograft placement on or before Week 12	
Missing/incomplete binary variable will be imputed as failure.

Objectives	Population	Hypotheses	Endpoints	Intercurrent events and data handling
To evaluate the mean averaged percent area of StrataGraft treatment sites autografted per subject by Week 12	All enrolled subjects who received StrataGraft	$H_{02}$ : Mean of averaged percent area of StrataGraft treatment sites autografted per subject by Week 12 $>50\%$ . $H_{12}$ : Mean of averaged percent area of StrataGraft treatment sites autografted per subject by Week 12 $<50\%$ .	Mean of averaged percent area of StrataGraft treatment sites per subject autografted by Week 12	

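### Section 12.3.1.2 contradicts itself for ranked secondary 3: the post-autograft censoring rule removes later grafts that the endpoint's own definition adds up

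*Combined protocol and SAP*

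**What the plan says.** All of the analysis text is in the combined protocol.

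- **Endpoint.** Section 12.3.1.2 lists ranked secondary 3 as "Mean of averaged percent area of StrataGraft treatment site autografted by Week 12". Table 8 has it as "Mean of averaged percent area of StrataGraft treatment sites per subject autografted by Week 12", with the alternative hypothesis that the mean is below 50%.
- **Definition.** A later paragraph of 12.3.1.2 divides the summed percent area by the number of sites on the subject and adds: "It is a cumulative sum of percent area autografted for all nonmissing visits on or before Week 12".
- **Censoring.** Between the list and that definition stands a paragraph on data handling for the ranked endpoints in general. It says "For continuous efficacy endpoints, missing data will not be imputed", and it closes with "If a subject has autograft placement, the data collected after the autograft placement will be censored". No endpoint is excepted there, in Table 8 or in Section 12.3.3.
- **Collection.** Section 10.3 records at each visit "Autograft placement on study treatment site since last study visit, noting area autografted, if any; placement is assessed until complete closure is noted", and Section 10.4 does the same at Week 12 and Months 6 and 12. Section 11.3.3 adds: "The area of each StrataGraft treatment site that is autografted will be measured during the autografting procedure".
- **Sites per subject.** Section 7.1 allows a treatment area "which may be composed of up to 3 non-contiguous areas located on the same extremity or plane of the torso".

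The separate SAP memo plans listings for the single enrolled subject and no formal analysis. It does not address the censoring rule.

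**The concern.** Censoring at autograft makes sense for an endpoint defined as closure without autograft. For an endpoint that measures the autograft itself, the same event both starts the measurement and cuts it off. A second session on the same site is collected after a placement. So, if the rule acts on the whole subject, is a first graft on another of the up to three sites. The censoring sentence removes these areas and the running-total sentence requires them.

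The primary objective (Section 5.1.1) is about eliminating or reducing the need for autografting. The primary endpoint and ranked secondaries 1 and 2 show whether, or how far, sites closed without a graft. Ranked secondary 3 is the only ranked endpoint that says how much graft was still used. The children affected are those grafted in stages or at several sites, so any loss falls on the least favourable outcomes.

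**Working it through.** **Plan's own figure.** None is stated for ranked secondary 3. The nearest is the primary endpoint's power, above 90% with 50 subjects, 83% assumed against 50% (Section 12.1). With success declared when the lower limit of the normal-approximation 95% CI is at least 50%, the smallest passing count is 32 of 50: 0.64 − 1.96 × √(0.64 × 0.36 / 50) = 0.507. Exact binomial power is 0.9997. For 40 subjects the smallest count is 26 and power is 0.998. The stated power is reproduced, and the counts 32 and 26 are used below.

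**Effect of the rule on one subject.** Let subject *i* have *k* sites, and let *a* be the newly grafted percent of a site at a session.

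- As defined: Y = (sum of *a* over all sites and all sessions to Week 12) / *k*.
- As censored: the same sum, stopped after the first session.
- Difference: (sum of *a* after the first session) / *k*. This is never negative, and it is zero for a child with no graft or one session.

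No censoring method is named for a mean with a t-based interval, and continuous data are not imputed, so a censored graft simply leaves the sum.

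**Illustrations (graft areas assumed; the documents give none).**

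| Subject | All grafts | Censoring by subject | Censoring by site |
|---|---|---|---|
| One site: 30%, later 50% of new area | 30 + 50 = 80% | 30% | 30% |
| Two sites: A 100% at Day 14, B 60% at Day 28 | (100 + 60)/2 = 80% | 100/2 = 50% | 80% |
| Three sites: 100% at Week 3, 60% at Week 5, none | 160/3 = 53.3% | 100/3 = 33.3% | 53.3% |

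The single-site case loses area on either reading. The multi-site cases lose it only if the rule acts on the whole subject.

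**Effect on the mean, N = 50.** Assume *g* children are grafted, each 30% first and 40% later, and the rest not at all. The mean is 70*g*/50 with all grafts and 30*g*/50 with censoring.

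| *g* | All grafts | Censored |
|---|---|---|
| 2 | 2.8% | 1.2% |
| 8 | 11.2% | 4.8% |
| 18 | 25.2% | 10.8% |

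These rows show the mechanism and are not a forecast.

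**Effect on the test.** Ranked secondary 3 is tested only after the primary endpoint succeeds, so at most 50 − 32 = 18 children can have been grafted. Take the extreme in which all 18 have 100% of their area grafted and no area is counted twice:

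- N = 50: mean 36.0%, SD 100 × √(0.36 × 0.64 × 50/49) = 48.5, upper 95% limit 49.8%, still below 50%.
- N = 40 (the early-closure option in Section 12.1): at most 40 − 26 = 14 grafted, mean 35.0%, upper limit 50.4%.

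Even with full counting, the upper limit passes 50% only at or very near the N = 40 extreme. Only there could censoring change the decision.

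**The case against.** The strongest reply is that the intended meaning is clear. The sentence specific to the endpoint comes after the general one, a sum over visits has little purpose if it stops at the first graft, and Sections 10.3 and 10.4 keep collecting grafted area until closure. The censoring sentence fits the two endpoints defined without autograft placement. This stands as evidence of intent, and it is why the point is a contradiction to reconcile and not a settled bias. It does not remove the defect: the censoring rule is unqualified, and a programmer following it would drop later grafts.

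Four stronger readings are tempting, and the documents do not support them.

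- **That the rule certainly cuts off all of a subject's sites.** The trigger is worded by subject, but the text does not say whether the data of other sites are included, and results are also to be shown by designated site.
- **That even the first graft is lost,** because visits record grafts already placed. Section 11.3.3 measures the area during the procedure, so keeping the first graft is the more natural reading.
- **That the mean is understated by a known amount.** Supposing staged grafting in 5% to 10% of children with 30 to 50 points lost each would give 1.5 to 5 points (0.05 × 30 to 0.10 × 50). No document gives such a rate. Section 6.2 reports that more than 95% of adult subjects closed without autografting; if that carried over, at most 2 of 50 children would be grafted at all. Nor can a 17% graft rate be read from the 83% in Section 4.2, because that figure counts missing data as failure.
- **That the test result is at risk.** The calculation shows it practically is not.

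It is also fair to say that no planned output is affected, since the SAP memo foresees listings only. One of them, Listing 16.2.5.6, covers additional autografting, with no censoring stated.

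**Conclusion.** The contradiction is real. As written, 12.3.1.2 both requires and removes grafts placed after the first session for ranked secondary 3, and nothing else in the protocol or the SAP memo resolves it. If the censoring sentence governs, the autografted area can only be understated, in the product's favour. For a single child the loss can be large (30% instead of 80% in the assumed single-site case). For the trial mean it cannot be sized from the documents. The conclusion about the test rests on the primary endpoint having succeeded, on the whole ITT population contributing a value, and on no area being counted twice. Under those conditions the harm is to the estimate and its interpretation, and hardly to the decision. The defect lies in the protocol's analysis plan and matters for the record and for any reuse of this section.

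**What to change.** In 12.3.1.2 and in the third row of Table 8, state that:

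1. Censoring after autograft placement applies only to the closure endpoints.
2. Ranked secondary 3 counts all autograft placed on any treatment site from StrataGraft application through Week 12, with re-grafted area counted once so that no site exceeds 100%.

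In the same place, say for the closure endpoints whether censoring applies to the grafted site alone or to the whole subject. On the whole-subject reading, an ungrafted site that closes after another site is grafted could be scored as a failure in ranked secondary 2, which would count against the product.

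The cost is a few sentences. Grafted area is already collected (Sections 10.3, 10.4 and 11.3.3), although counting re-grafted area once requires the record to separate new from re-grafted area. The reported autografted area may become slightly less favourable. The listings in the SAP memo need no change.

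### The post-autograft censoring rule in Section 12.3.1.2 works by subject, but ranked secondary 2 counts sites; read literally, ungrafted sites that close after another site's graft lose their closure

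*Combined protocol and SAP*

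**What the plan says.** All section numbers refer to the protocol unless the SAP is named.

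- **Censoring rule (Section 12.3.1.2):** "If a subject has autograft placement, the data collected after the autograft placement will be censored". It does not limit the data to the grafted site, and no other section gives a rule for data after a graft.
- **Endpoint (Section 12.3.1.2):** ranked secondary 2 is "Number (%) of confirmed complete wound closures of the StrataGraft treatment sites on or before Week 12 without autograft placement". Its formula is "sites with confirmed complete wound closure without autografting on or before Week 12/Total number of treatment sites) x 100". The unit is the site and the denominator is every treatment site.
- **Sites per child (Section 7.1, inclusion criterion 7):** the treatment area "may be composed of up to 3 non-contiguous areas located on the same extremity or plane of the torso".
- **Missing binary data:** Section 12.3.1.2 says "Missing or incomplete binary variables will be imputed as failures", and Table 8, row 2, says "Missing/incomplete binary variable will be imputed as failure". Section 12.3.3 says the opposite for the ranked secondary endpoints: no imputation.
- **Confirmation (Section 12.3.1.1):** closure must be seen at two consecutive visits at least 2 weeks apart, no later than Week 20, and is dated to the earlier one.
- **SAP memo:** one subject was enrolled, no formal analyses will be done, and only listings are planned. It does not take up the censoring rule.

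**The concern.** The rule and the endpoint use different units. Once one site on a child is grafted, the literal rule sets aside later data on all of that child's sites, including sites that were never grafted and went on to heal. Those sites are what ranked secondary 2 sets out to count.

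Two analysts could then report different numbers from the same data, one following the censoring sentence and the other the formula. Under the censoring sentence the site closure rate is too low, for a reason unrelated to the healing of the site being counted.

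**Working it through.** **The plan's own figure.** No power or expected rate is given for ranked secondary 2. The only stated figure is for the primary endpoint: over 90% power with 50 subjects, null 50%, true rate 83% (Section 12.1). The smallest passing count is 32/50, since 0.64 − 1.96 × √(0.64 × 0.36/50) = 0.507. Exact binomial power is 99.97%, so the statement holds. It does not bear on the censoring rule.

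**Worked child.** Three sites. A is autografted at Week 4. B and C are first closed at Week 6 and confirmed at Week 8, with no graft.

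| Step | Rule applied by subject | Rule applied by site |
|---|---|---|
| Site A | not closed without autograft | not closed without autograft |
| Sites B and C | Week 6 and Week 8 data set aside | both confirmed closed |
| Numerator / denominator | 0/3 | 2/3 |

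The imputation rule does not change the first column. Under Section 12.3.1.2 and Table 8, B and C are incomplete and count as failures. Under Section 12.3.3 they are not imputed, but they still have no usable closure, and the formula divides by all treatment sites.

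A site confirmed closed before the graft keeps its success. A site first seen closed before the graft but due for confirmation after it loses its success, because confirmation takes at least 2 weeks.

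**Size, illustration 1 (expected values).** The documents give neither the number of sites per child nor the graft rate, so every input except 50 and 83% is an assumption, and using 83% for single sites is one too. Let f be the share of children with several sites, m the sites each of them has, and g the share of those children with one site grafted early. The other sites close with probability 0.83, all after the graft.

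- Total sites = 50(1 − f) + 50fm
- Closures lost = 50 × f × g × (m − 1) × 0.83
- Loss in the rate = closures lost / total sites

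| f | m | g | Total sites | Closures lost | By site | By subject | Loss (points) |
|---|---|---|---|---|---|---|---|
| 0.2 | 2 | 0.05 | 60 | 0.415 | 82.3% | 81.6% | 0.7 |
| 0.4 | 2 | 0.17 | 70 | 2.82 | 79.0% | 74.9% | 4.0 |
| 0.6 | 3 | 0.30 | 110 | 14.94 | 76.2% | 62.6% | 13.6 |

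**Size, illustration 2 (simulation, 20,000 children per scenario).** Assumptions: 60/30/10% of children with 1/2/3 sites, grafts at Weeks 3 to 6, within-child correlation 0.5 on the latent scale, median closure at Week 4, confirmation 2 weeks later.

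| Sites grafted | By site | By subject | Loss (points) |
|---|---|---|---|
| 5% | 94.7% | 92.4% | 2.3 |
| 10% | 89.7% | 85.5% | 4.2 |
| 15% | 84.8% | 79.6% | 5.2 |

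With a 40/40/20% mix the losses are 3.2, 5.6 and 7.4 points. With one site per child the loss is zero.

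**Effect on the test against 50%.** Take the worst row of illustration 1, 62.6% of 110 sites. Treating sites as independent, the lower 95% limit is 0.626 − 1.96 × √(0.626 × 0.374/110) = 0.536. If sites within a child were fully correlated, so that only 50 units count, it is 0.626 − 1.96 × √(0.626 × 0.374/50) = 0.492. Only that extreme corner comes near 50%.

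**The case against.** **Censored is not defined as missing.** This stands as a limit. Section 12.3.1.2 expects missing data only from loss to follow-up and never says what censoring means for a binary endpoint. A reader might infer that the plan openly scores these ungrafted sites as failures. It does not; that step is an inference. The count is the same without it, because the formula's denominator is fixed at all treatment sites. Only dropping the sites from the denominator would avoid the loss, and the formula gives no basis for that.

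**The authors probably meant the grafted site.** This is plausible. The objective, hypothesis, endpoint and formula are all by site, and Section 12.3.1.3 counts subjects within a designated site, so the word subject may be loose. A fully literal reading would let a graft on a non-study burn trigger censoring too, which is hardly intended. But no sentence limits the rule to the grafted site, and the SAP memo does not settle it.

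**The size rests on chosen inputs.** This also stands. Section 6.2 reports that more than 95% of adult subjects closed without autografting. That is adult, subject-level evidence, but it points to the low end. The 10% and 15% graft rates have no support in the documents.

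**Nothing turns on it.** Largely right: the bias is conservative, and no analysis will be run.

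**Conclusion.** The point holds as a mismatch of units in the protocol's analysis text. Read literally, the censoring sentence removes closures of ungrafted sites that the endpoint's own formula counts, under either imputation rule.

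The direction is downward for ranked secondary 2. The size is illustrative only: about 2 points if 5% of sites are grafted, more with higher graft rates or more multi-site children, and none if every child has one site.

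Two stronger readings are not supported. One is that the error threatens the conclusion of the test against 50%: at plausible inputs the rate stays far above 50%. The other is that it damages the main result: the primary endpoint already requires every site to close without autograft, so a child with a grafted site has failed whatever the other sites do. With one subject enrolled and listings only, no reported result changes.

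Severity: low.

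**What to change.** For ranked secondary 2, replace the sentence in Section 12.3.1.2 with:

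> *If a StrataGraft treatment site is autografted on or before Week 12 and before its closure is confirmed, data collected on that site after the autograft are not used to show closure and the site counts as not closed without autograft. Data on the subject's other, ungrafted treatment sites continue to be used.*

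The two time limits matter. Without them, a site confirmed closed at Week 8 and grafted at Month 6 would become a failure. Naming the treatment site also rules out a trigger from grafts on non-study burns.

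Carry the same wording into Table 8, row 2. Align Section 12.3.3, which now contradicts Section 12.3.1.2 and Table 8 on imputation for this endpoint. The present sentence also covers ranked secondaries 1 and 3, so each needs its own statement of how data after a graft are used; the wording above is for ranked secondary 2 only.

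The cost is a few sentences. No new data are needed: each site is assessed separately at every visit (Sections 10.3 and 10.4), and grafted area is measured for each site (Section 11.3.3). If the protocol text is not reused, no action is required for the present study.
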